### 2.1 Study Objects

#### 2.1.1 Primary Objective

- Blood loss of the subjects in 5 days post operation

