#### 4.5 Methods of Minimizing Risk and Bias

Using a third party to hide the grouping will help reduce the errors caused by selection. The randomization will be proceed in operation, and the staff should set blinding to the subjects.

Operational errors could result in change in blood transfusion rate. To minimize this risk, we need to make sure that all operating rooms and recovery wards in each center use an unified blood transfusion plan. Each medical team within each center should have same start-up criterion for setting up blood transfusion. Before participating in the trial, each center should provide a blood transfusion plan to the leader center for record. Some centers would use a prespecified value of Hb to determine whether blood transfusion is needed and this value should be unified among each center's medical team. If any of the following symptoms presents, such as unconscious, dyspnoea, exhaustion, which could clearly indicate level of red cell, blood transfusion is needed. Maternal mobility and neonatal care after cesarean section are different from the postoperation rehabilitation activity of most bedridden patients. According to the practical issues, since the clinicians may have different point of view, it is allowed to have little variation between each center. It represents the difference in reality cross the clinic, so it will not increase the bias.

Postpartum ward medical staff should use an unified blood transfusion plan as far as possible, according to the postoperative Hb levels and maternal symptoms. Do not deliberately observe the grouping of subjects.

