## 4.7 Treatment Plan

According to local transfusion guidelines and medical staff's opinion (participant's Hb is lower than 70g/L before transfusion, or Hb is between 70~100g/L, depending on transfusion plan and medical staff.), women will be randomly allocated to either:

1. Caesarean section with IOCS(treatment group)
2. Caesarean section without IOCS. eg. donor blood transfusion(control group)

Theoretically, intraoperative blood transfusion need to be based on the following formula:

the volumn of blood transfusion needed(ml) \* Hb of transfusion samples =  $(Hb_2 - Hb_1) * \text{blood volumn}$ ,

where  $Hb_1$ :actual Hb;  $Hb_2$ : target Hb(100g/L)

blood volumn =  $100\text{ml/kg}^{10} * \text{weight}$

Either in treatment group or control group, the difference between the actual volumn of blood transfusion and the theoretical volumn should be controlled within  $\pm 15\%$  (in terms of mass of Hb).

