## 8.2 Outcomes

### 8.2.1 Primary Outcomes

- Blood loss post operation

Hb and Hct in first and fifth day after surgery.

The direct measurement of is the accurate volume of blood loss in major haemorrhage is difficult. Alternatives such as haemoglobin (Hb) or hematocrit (Hct)

are more frequently used and blood loss can be calculated using these parametres. Since Hct or Hb will be recorded as per standard practice during and postoperative in the hospital.

In this proposed trial, we are planning that Hb and Hct in the first and fifth day after the surgery as the primary outcome to reflect the blood loss.

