### 8.2.2 Secondary Outcomes

- PT/APTT, Hct and Hb in first and fifth day after surgery
- the number of units of donor blood transfused
- mean fall in serum haemoglobin level
- maternal morbidity resulting from postoperative anaemia
- time to first mobilisation,
- duration of hospital stay
- immediate multidimensional fatigue inventory.
- Total cost in hospital

Second Stage: Follow-up when pregnancy again:

Neonatal hemolytic disease (Appendix 2)

Determine blood type, antibody, and IgG titer)

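### The primary outcome is day-1 and day-5 Hb and Hct with no allowance for ward transfusion between the samples, so it understates blood loss in the women transfused

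*Combined protocol and SAP*

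**What the plan says.** **Objective and test.** Section 2.1.1 gives the primary objective as "Blood loss of the subjects in 5 days post operation". Section 8.3.3 frames the hypothesis and the decision rule in terms of the amount, and the median amount, of blood lost.

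**Outcome.** Section 8.2.1 carries a blood-loss heading and remarks that "blood loss can be calculated using these parametres", but gives no formula. It then settles on "Hb and Hct in the first and fifth day after the surgery as the primary outcome to reflect the blood loss". Section 8.2.2 lists Hb and Hct on the same two days again as secondary outcomes, together with "mean fall in serum haemoglobin level".

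**Sizing.** Section 8.1.1 computes pilot blood loss as blood volume times the Hct difference between day 1 and a later day x, plus Vt, the volume of red cells. Neither 8.2.1 nor 8.3 refers to this formula.

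**Transfusion.** In theatre (4.7), both arms are transfused by formula towards a target Hb of 100 g/L. The tolerance is ±15%, in mass of Hb: "Either in treatment group or control group, the difference between the actual volumn of blood transfusion and the theoretical volumn should be controlled within" that margin. After surgery (4.5): "Postpartum ward medical staff should use an unified blood transfusion plan as far as possible, according to the postoperative Hb levels and maternal symptoms". The trial is single-blind. Ward staff are asked not to go looking for the allocation, but nothing conceals it from them.

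**The concern.** Hb and Hct respond to blood lost and to red cells given. On the ward, a low Hb is itself one of the triggers for transfusion, and transfusion then raises the value that is read on day 5. The women who bleed most after the day-1 sample are the most likely to have their fall in Hb reversed before it is measured.

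Two things are at stake:

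- If one arm bleeds more and is transfused more on the ward as a result, a real difference in loss shrinks in the Hb or Hct change.
- If the arms bleed equally but unblinded staff transfuse one more readily, the outcome shows a difference in loss that does not exist.

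**Working it through.** **Inputs.** Blood volume 100 ml/kg, target Hb 100 g/L, tolerance ±15% (4.7). Donor red cells 240 g/L, about 200 ml per unit, example woman of 60 kg with Hb 60 g/L (4.7, part b). Pilot SD 709 ml, delta 200 ml, formula loss = BV × (Hct day 1 − Hct day x) + Vt (8.1.1).

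**1. The plan's own figures.**
- BV = 100 × 60 = 6000 ml = 6 L. Hb mass needed = (100 − 60) × 6 = 240 g. At 240 g/L that is 1000 ml, as the plan states.
- Sample size: (1.96 × 709 / 200)² = 48.28, so 49, against a stated 50 (t quantiles give 51). 50 × 1.2 = 60 per arm, 120 in total. These reproduce closely enough. The 8.1.1 formula is a precision formula for one mean; its 200 ml serves here only as the yardstick that the plan supplies.

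**2. One ward unit in Hb terms.** 0.2 L × 240 g/L = 48 g. 48 / 6 = 8 g/L at 60 kg. The range is 48 / 5 = 9.6 g/L at 50 kg to 48 / 8 = 6.0 g/L at 80 kg.

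**3. One ward unit on the loss scale.** Rearranging the formula, BV × (fall in Hct) = loss − Vt. Assume a loss of 400 ml between the samples at 60 kg, and count each unit as 200 ml of Vt:

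| Ward units | Fall in Hct | BV × fall | With Vt added |
|---|---|---|---|
| 0 | 0.067 | 400 ml | 400 ml |
| 1 | 0.033 | 200 ml | 400 ml |
| 2 | 0.000 | 0 ml | 400 ml |
| 4 | −0.067 (a rise) | −400 ml | 400 ml |

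The last column is constant by construction. The third column shows what is lost when Vt is left out: 200 ml per unit, and 200 / 200 = 1.0 times delta.

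**4. Theatre transfusion.** In the worked example ±15% of 240 g is ±36 g, or ±6 g/L, so Hb after transfusion may lie between 94 and 106 g/L at identical loss. This precedes the day-1 sample. It shifts the day-1 and day-5 levels together but is not part of the change between them.

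**5. Between arms.** Unadjusted difference = true difference in mean loss − difference in mean Vt. If the arms differ by d ward units per woman, the shift is 200 × d ml. The documents give no value for d, nor its sign.

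**The case against.** The strongest reply is that the plan already contains the correction. The objective, the hypothesis and the sample size are all in terms of blood loss. The formula in 8.1.1 adds red cells back, and the two Hct values in 8.2.1 look like its inputs with x = 5. On that reading a raw-Hb analysis would contradict the rest of the plan, and 8.2.1 merely lacks a cross-reference. Part of this stands: a reader might infer that the sponsor has chosen to analyse uncorrected Hb, and the documents do not show that. But 8.2.1 is the section that defines the outcome. It names Hb and Hct and adopts no formula, and 8.1.1 leaves both x and the transfusions counted in Vt open. An analyst who follows 8.2.1 literally would leave transfusion out.

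The plan also has safeguards: a common ward transfusion plan as far as possible, stratification by centre, daily recording of transfusion, and donor units as a secondary outcome. These limit or reveal differences in transfusion. They do not remove its effect from the primary variable.

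It is also fair to say that fall in Hb has its own clinical interest, given the anaemia rationale in section 1. That supports keeping it as a secondary outcome without adjustment.

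**Conclusion.** The point holds as a defect in the definition of the primary outcome. As written, 8.2.1 makes no allowance for transfusion, and ward transfusion between the two samples lowers the apparent loss by about 200 ml per donor unit, the whole planning delta. In Hb it is about 8 g/L at 60 kg. This rests on the plan's own constants and on counting a full 200 ml unit as Vt.

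Three stronger readings are not supported:

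- A reader might convert a unit's 48 g of Hb into 480 to 600 ml of whole blood at Hb 100 to 80 g/L and call that 2.4 to 3 times delta. Delta was set on the 8.1.1 scale, where blood volume is multiplied by an Hct difference and red-cell volume is added. On that scale the ratio is 1.0.
- A reader might infer that transfusing both arms to one Hb target in theatre hides postoperative loss. It mainly affects absolute Hb and Hct, not the change from day 1 to day 5.
- A reader might infer that the trial is biased towards a particular arm. Neither the size nor the direction of net bias can be computed from the documents.

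**What to change.** In 8.2.1 and 8.3, define the primary outcome as calculated postoperative blood loss in ml from day 1 to day 5, using the 8.1.1 formula with x = 5. Define Vt as all red cells, donor and salvaged, given between the day-1 and day-5 samples. State how volumes are put on one scale, since the examples in 4.7 take donor cells at 240 g/L and salvaged blood at 200 g/L.

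Keep Hb, Hct and mean fall in Hb as secondary outcomes, reported beside ward units transfused by arm, and say that similar Hb between arms is not evidence of similar blood loss. Use the directly measured postoperative loss of 4.9.1 as a supportive analysis. It is not the better primary, because 8.2.1 itself calls direct measurement difficult in major haemorrhage and the weighing also passes through unblinded staff.

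The cost is small. The change is to outcome and analysis wording and touches no transfusion rule; the procedure table in 4.8 already has daily bleeding and transfusion recorded. The calculated loss depends on an assumed blood volume and on complete transfusion records. The case report form should make clear which units fell between the two samples.

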### 8.2.2 Secondary Outcomes

- PT/APTT, Hct and Hb in first and fifth day after surgery
- the number of units of donor blood transfused
- mean fall in serum haemoglobin level
- maternal morbidity resulting from postoperative anaemia
- time to first mobilisation,
- duration of hospital stay
- immediate multidimensional fatigue inventory.
- Total cost in hospital

Second Stage: Follow-up when pregnancy again:

Neonatal hemolytic disease (Appendix 2)

Determine blood type, antibody, and IgG titer)

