## 4 Study Procedure

### 4.1 Flow Chart of Study

### 4.2 Informed Consent Acquisition Process

#### 4.2.1 Elective Cesarean Section

Selected maternal in cesarean section will receive detailed information. They will

also have the opportunity to ask questions after the appointment of surgery. The paper version informed consent will also be obtained on the day of admission to the ward or the day of operation. The informed consent forms need to make it clear that they can withdraw from the trial at any time for any reason, without discrimination and without any justification for their withdrawal from the trial. Randomization will be carried out on the day of operation.

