### 4.3 Patient Screening Process

Researchers need to understand the situation of new hospitalized maternal, such as the presence of potential subjects. Researchers also need to read their medical case reports in detail, and then confirm the inclusion criteria and exclusion criteria. When all the criteria meet, we need to get informed consent from potential subjects, and informed consent needs to be obtained prior to surgery. After receiving the informed consent, randomization will be performed directly in the delivery room at the time of preparation (in order to provide enough consideration to maternal time) and subjects will be assigned to the respective groups based on randomization results. The screening process needs to be recorded in the patient enrollment form.

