### 4.4 Randomization Process

Once subjects are confirmed through all the criteria and have received the informed

consent, they can be randomized to either the treatment group(Caesarean section with IOCS) or control group(Caesarean section without IOCS).The randomization will be proceed in operation if the patient needs blood transfusion.

Randomization (ratio:1:1) is used through a network-based randomization system, which follows SOP. We use central dynamic randomization system.

The randomization will be stratified by 5 conditions:

1. centers
2. type of cesarean section (Emergency/Elective)
3. whether there exist abnormality in placental
4. number of fetus (twins or more)
5. whether the ASA level is in I – II?

The randomization system will be tested and validated before the trial starts and will be supervised by the leader center's CRA and statistical expert throughout the trial. Once the subjects have been successfully grouped, they will be recorded in the enrollment form.

Each test center has their independent account and password for randomization system. The account number and password are authorized to the relevant staff by the major researchers in each center. After the staff has filled in the subject's ID and details into the randomization system, the system will display the grouping result.

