#### 4.8 Procedure Table

	Preoperative	Intraoperative	Postoperative	Hospital Discharge	Long-term Follow-up
Eligible criterion and Grouping					
Inclusion, exclusion criteria review	X				
Informed Consent Acquisition	X				
Record demographic information, contact info, diagnosis, type of surgery, cesarean section indication, birth history, preoperative blood loss, comorbidities (past history), blood group ABO, and other abnormalities		X			
Randomization (Dynamic Randomized)			X		
Blood Transfusion					
Intraoperative blood transfusion and other blood products		X	X		
Intraoperative autologous blood transfusion, and related data		X			
Maternal					
Intraoperative anesthesia operation time, special circumstances (such as hypotension), urine output		X			

Intraoperative and postoperative daily bleeding and transfusion, infusion volume (crystal, gel), blood-related drugs		X	X		
The highest body temperature, Hb / Hct / Plt, PT / APTT, ALT / AST / total G / D and renal function (creatinine and urea)	X	X	X		
Postoperative bleeding (drainage, bleeding, lochia, etc.)			X		
Specific causes of postoperative bleeding (uterine inertia, placental conditions, soft birth canal laceration situation)			X		
Test of blood component in recover blood and maternal blood fetal		X (Specimen only)	X (Specimen only)		
Transfusion reaction		X	X		
Other hospitalization					
Time to first mobilisation			X		
Duration of hospital stay				X	
Intraoperative and postoperative adverse events		X	X		
Reoperation caused by bleeding			X		
Inpatient mortality				X	
Overall medical expenses				X	
Tracking for hemolytic disease in future birth					X

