## 8.3 Statistical Methods

### 8.3.1 General Principle

Using SAS 9.13 for statistical analysis. All statistical tests should be two-sided. If p-value is less or equal to 0.05, then it is considered to be statistically significant.

Variables data are described by mean±standard deviation, median, maximum and minimum. Use paired t-test to compare intra-group variations with respect to baseline and use ANOVA or Wilcoxon rank-sum test to compare variations between groups.

Attributes data are described as frequency (percentage). Between group comparison of percentages is tested by Fisher's exact test

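### Hospital cost has no prespecified mean-difference analysis: the plan allows ANOVA or a rank-sum test without a rule for choosing, and the rank-sum test does not address mean cost

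*Combined protocol and SAP*

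**What the plan says.** Table 1 lists, as its third objective, whether routine cell salvage is cost-effective against current practice. Section 2.2 (Study Design) repeats that the trial includes a cost-effectiveness analysis.

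Section 8.2.2 names two resource outcomes, "duration of hospital stay" and "Total cost in hospital". In the Procedure Table (section 4.8) the stay and a single item, "Overall medical expenses", are both marked in the hospital discharge column. No start point, list of cost items or price basis is given for either.

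The only analysis instruction that reaches cost is in section 8.3.1. Continuous variables are described by mean, SD, median and range, and for group comparisons the plan is to "use ANOVA or Wilcoxon rank-sum test to compare variations between groups". It does not say what decides between the two tests, and it makes no exception for cost. Section 8 contains no other economic method.

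On timing, section 4.4 states: "The randomization will be proceed in operation if the patient needs blood transfusion". Section 4.3 instead says "randomization will be performed directly in the delivery room at the time of preparation", and section 4.2.1 says "Randomization will be carried out on the day of operation". These do not agree on the moment, but all of them fall after admission. Section 4.2.1 also treats admission and operation as days that may differ: "The paper version informed consent will also be obtained on the day of admission to the ward or the day of operation".

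**The concern.** An economic comparison needs the difference in arithmetic mean cost, because the mean multiplied by the number of women gives the total bill. ANOVA addresses that quantity. The rank-sum test asks whether costs in one arm tend to rank above those in the other. With skewed costs of different spread, the two questions can have different answers. Cell salvage could plausibly change the spread of cost as well as its level, by adding a fairly fixed equipment cost and altering how often a long and expensive course occurs. That is the setting in which the tests part company.

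Because the choice is open, it could be made after the data are seen. A significant rank-sum result might then be reported as a cost saving when mean costs are equal, or when the mean is higher in the arm that appears cheaper. A real difference in means could equally be missed.

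The secondary issue is the window. Days and charges that precede randomisation cannot respond to the allocated arm. Including them adds variation to the comparison without adding information about the intervention.

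**Working it through.** **The plan's own figure.** The documents give no mean, SD, target difference or power for cost or stay. The only sample-size calculation is for blood loss (section 8.1.1): (1.96 × 709 / 200)² = 48.28, or 49 rounded up. The plan states 50, then 50 × 1.2 = 60 per arm and 120 in total. This reproduces to within rounding and supplies only the 60 per arm used below.

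**Rank-sum test against the mean.** Assumptions, not in the documents: costs are lognormal, with log-SD s₁ in arm A and s₂ in arm B, and 60 women per arm. Tests are two-sided at 0.05, as in section 8.3.1.

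A lognormal mean is exp(μ + s²/2), so with equal means the log-means differ by (s₂² − s₁²)/2. The chance that a random woman in B costs less than one in A, which is what the rank-sum test responds to, is Φ[(s₂² − s₁²)/2 ÷ √(s₁² + s₂²)].

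- s₁ = 0.5, s₂ = 0.8: Φ(0.195 / 0.943) = Φ(0.207) = 0.58.
- s₁ = 0.5, s₂ = 1.0: Φ(0.375 / 1.118) = Φ(0.335) = 0.63.

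Both exceed 0.5 although the mean costs are identical. Rejection rates from 4,000 simulated trials per scenario (the two-group t-test is equivalent to ANOVA here):

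| True situation | Log-SDs | Rank-sum rejects | ANOVA rejects |
|---|---|---|---|
| Equal means, same shape | 0.5, 0.5 | 5% | 5% |
| Equal means | 0.5, 0.8 | 34% | 5% |
| Equal means | 0.5, 1.0 | 71% | 7% |
| Equal medians, mean ratio 1.22 | 0.5, 0.8 | 5% | 21% |
| Equal medians, mean ratio 1.46 | 0.5, 1.0 | 6% | 46% |

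A separate run of 10,000 trials gave 34% and 70% for the two equal-mean rows with unequal spread. In the same run, arm B had a true mean 10% higher (log-SDs 0.5 and 1.0). The index becomes Φ[(0.375 − ln 1.1) / 1.118] = Φ(0.250) = 0.60, and the rank-sum test significantly favoured the dearer arm in 46% of trials.

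The first row matters as well: when the two shapes are the same, the rank-sum test keeps its 5% error rate.

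**Window.** Write total = pre-randomisation part + post-randomisation part, assume the two are independent, and let the SD of the first be k times that of the second. The variance of the total is then 1 + k² times that of the post-randomisation part. The value of k is not in the documents.

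- k = 0.25: 1 + 0.0625 = 1.06; SE × 1.03; 60 per arm has the precision of 60 / 1.0625 ≈ 56.
- k = 0.5: 1 + 0.25 = 1.25; SE × 1.12; 60 / 1.25 = 48.

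For an effect with 80% power on the post-randomisation part alone, power becomes Φ(2.80 / √(1 + k²) − 1.96), which is 78% at k = 0.25 and 71% at k = 0.5.

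The expected pre-randomisation part is the same in both arms, so the expected difference in means does not change.

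**The case against.** ANOVA is one of the two permitted tests and it compares means. Arm means and SDs are to be reported in any case, so a reader could form the mean difference from planned output. The rank-test fault therefore arises only if that branch is chosen, and nothing in the documents shows that it will be. This stands, and it makes the fault conditional. It does not supply a choice rule, an estimate or an interval for an outcome tied to a stated objective.

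A reader might infer that stay and cost are defined from admission. The documents do not say so. The discharge column in section 4.8 shows when the items are recorded, not the period they cover. Where the protocol does quantify hospitalisation, in the serious adverse event rules (sections 7.1.2 and 7.4), it counts from the caesarean section. That is a safety definition and does not settle the outcome, but it weakens the inference for stay. For cost, the words total and overall make inclusion of earlier spending the plain reading.

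A reader might also suppose that women spend long antenatal periods in hospital, so that the noise is large. No length of stay before operation is given, and the pre-operative part may be small. Finally, total hospital cost is a legitimate quantity, and section 1.2 expresses interest in overall maternal costs. It should still be reported.

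**Conclusion.** The point holds for the cost analysis. The plan promises an economic comparison but leaves cost to a choice between two tests that answer different questions, with no rule and no planned estimate of the mean difference. The simulated error rates (34% and about 70% against a nominal 5%) rest on assumed lognormal shapes with unequal spread. They show what the rank-sum branch can do and do not predict this trial's result.

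The window point holds in a limited form: the start of stay is undefined, and total cost probably includes spending that allocation cannot affect. The consequence is lost precision. A reading that the whole-admission window biases the comparison is not supported, and neither is any specific figure for the loss, since k is assumed.

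These are secondary outcomes, and the conclusion on blood loss is untouched. The change should be made because it is cheap and the cost result answers a declared objective.

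**What to change.** 1. In section 8.3, name the cost analysis: the between-arm difference in arithmetic mean cost, with a bootstrap 95% confidence interval. State that no rank test will be used for cost. Medians may stay as description.
2. Define stay as time from operation or randomisation to discharge, and reconcile sections 4.3 and 4.4 on when randomisation occurs so that the starting point is unambiguous.
3. Where dated bills are available, analyse cost from the day of operation, or adjust the total for the pre-operative part. Report the whole-admission total alongside. Charges from the operation day will still include some theatre and preparation spending before an intraoperative randomisation, which can be accepted and stated.

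Item 1 and the definition of stay need only wording. Item 3 needs a small CRF change, because section 4.8 collects one overall expense figure and the bill would have to be split at the operation date. If a centre cannot split its bills, item 1 can still be applied to the total, with some loss of precision.
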